### 1.2 C-UREA BREATH TEST

The C-urea breath test is based upon a modification of existing breath testing technology that detects and monitors a biomarker associated with peptic ulcers. The mechanism of action for detecting urease-containing bacteria in the lungs is the same as for detecting another urease-containing bacterium, *Helicobacter pylori*, in the stomachs of patients with peptic ulcers.

For the intended indication, inhaled C-urea is catalytically hydrolyzed into C-carbon dioxide by urease, an enzyme associated with certain bacterial pathogens common to lung infections in patients who develop CF (**I**).

$$^{13}$$
CO(NH2)2 + 3H2O  $\xrightarrow{\text{urease}}$   $^{13}$ CO2 + 2NH4OH (I)

By measuring the ratio of two stable and naturally occurring isotopes of carbon in exhaled carbon dioxide before and after inhalation of  $^{13}$ C-urea, the presence of urease-containing bacteria can be confirmed. In the absence of urease-containing bacteria in the lungs, the isotopic ratio of  $^{13}$ C to  $^{12}$ C in the baseline and test breath samples will be approximately the same. If urease-containing bacteria are present within the lungs, the concentration of exhaled  $^{13}$ C will be increased measurably in the test breath sample relative to baseline. It is not anticipated that the identity or numbers of organisms in the lungs can be deduced from the numerical  $\delta$  value reported by the breath test, but it is anticipated that the magnitude of the numerical  $\delta$  value will reflect the underlying bacterial load. It is anticipated that urease-producing bacteria can be detected within 15 minutes of initiating the breath test.

## 1.3 UREA

Urea has been approved by the Food and Drug Administration (FDA) for oral administration (75 mg when labeled with C) in the diagnosis of *H. pylori* infection in the stomach and for intravenous administration in high doses (500 to 1500 mg/kg/day, up to 120 g/day) as an osmotic diuretic to treat patients with cerebral edema and glaucoma. There is a significant amount of safety and toxicology data of urea administration via these routes (Crews and Davidson 1961, Crews and Davidson 1962, Gisbert and Pajares 2005, Pathak et al 2004, Pathak et al 2010, Soupart and Decaux 1996).

Urea liquefies viscid mucus when injected into the auditory canal (Bauer 1970) and is capable of reducing mucus viscosity and increasing mucus expectoration in lung diseases such as chronic obstructive pulmonary disease (COPD), bronchiectasis, CF, and asthma when administered by inhalation.

No adverse effects on lung function were reported when 2 to 14 g of urea was administered daily by inhalation with an intermittent positive-pressure ventilator over "short intervals" for 14 to 30 days to 32 patients with chronic bronchitis, cystic fibrosis, asthma, bronchiectasis, and emphysema; and no adverse effects were reported when approximately 7.3 g of urea was administered by inhalation over 10 minutes to 6 patients with CF using a DeVilbis nebulizer (assuming 6 mL 2M urea/min) (Waldron-Edward and Skoryna 1966).

The mucolytic properties of urea have not been pursued, however, because hypertonic solutions were subsequently shown to be a broncho-constrictor in patients with asthma (Cade and Pain 1972, Pain and Denborough 1967). In one such study, mean forced expiratory volume in 1 second (FEV1) decreased  $12\% \pm 20\%$  in 56 adults who inhaled urea aerosolized using a Wright nebulizer (Cade and Pain 1972). It is estimated that approximately 32 mg of urea was inhaled by each patient in this study assuming typical values of parameters of operation (output,

0.13 mL/min; airflow, 9 L/min) and reported experimental detail (urea concentration, 4M; inhalation time, 10 min).

It is now known that inhalation of osmotic agents such as urea, mannitol, and hypertonic saline cause the release of mast cell mediators (histamine and leukotrienes) in patients with asthma, resulting in bronchospasm (Anderson 2010, Brannan et al 2003, Brannan et al 2009, Sverrild et al 2009). Hypertonic saline has been used as a test for bronchial hyper-responsiveness in patients with asthma, and is widely used, nonetheless, with preventive bronchodilator administration to treat hyper-responsive patients with CF.

Overall, evidence points to the safety of inhaled urea. As with all inhaled solutions, it is possible that it will trigger some cough and bronchospasm; this does not occur in all subjects, however, and when it does occur, it is mild and transient. Further, pretreatment with a bronchodilator (albuterol) has been shown to prevent the response in most subjects. When bronchospasm does occur, it also can be rapidly reversed with albuterol therapy.

## 1.4 RATIONALE

It is anticipated that rapid detection and monitoring of lung pathogens will provide an early warning signal of the onset of bacterial load and early confirmation of the therapeutic effect of the treatment regimen. In laboratory experiments, urease-producing bacteria were detected within approximately 15 to 20 minutes after exposure to urea.

### 1.5 BENEFIT-TO-RISK ASSESSMENT

The safety profile of C-urea 20 mg and 50 mg administered by inhalation will be assessed in a dose escalation study conducted in two parts at a single center located at

University of New Mexico Hospital Pediatric/Adult Pulmonary Clinic Ambulatory Care Center [name]

This facility has the required equipment/protocol on site to respond to an emergent adverse effect of treatment. Co-investigators [name] or [name] will be available on site should an emergent adverse event (such as severe bronchospasm or cardiopulmonary arrest) occur during study administration.

This is the first study in humans of this C-urea breath test. In part 1, a conventional dose-escalation study design will assess the safety of inhaled C-urea in healthy volunteers. The maximum dose administered will not exceed 50 mg, which approximates the lowest estimated dose (32 mg) studied in humans (Cade and Pain 1972). In part 2, the same dose-escalation study design will assess the safety of inhaled C-urea in subjects with CF.

Thus, the risk to subjects enrolled in this study is small; there is no direct benefit to subjects who enrolled. The potential benefit of an early warning of accelerated colonization of bacteria that compromises or destroys lung function that may extend or save lives is significant.

# 2. OBJECTIVES

## 2.1 PRIMARY OBJECTIVE

The primary objective is to assess the safety of C-urea administered to healthy volunteers and subjects with CF by inhalation.

## 2.2 SECONDARY OBJECTIVES

The secondary objective is to assess the kinetics of C-carbon dioxide production by measuring the isotopic ratio of C to C in exhaled carbon dioxide up to 15 minutes after administration.

# 3. INVESTIGATIONAL PLAN

## 3.1 OVERALL DESCRIPTION OF STUDY DESIGN AND PLAN

# 3.1.1 Primary Endpoint

The primary endpoint is the safety of inhaled C-urea in healthy volunteers and in subjects with CF assessed by adverse events, spirometry test results (FEV1 and forced vital capacity [FVC]), and respiratory examinations (respiratory rate, auscultation [presence of wheezing and crackles], pulse oximetry, and related symptoms, such as cough).

# 3.1.2 Secondary Endpoint

The secondary endpoint is the isotopic ratio of C to C in exhaled carbon dioxide of healthy volunteers and in subjects with CF measured with the POCone detector (Meretek Diagnostics Group of Otsuka America Pharmaceutical, Rockville, MD) before study drug administration and at 5, 10, and 15 minutes after study drug administration.

# 3.1.3 Study Design

This is a single-center, single-administration, dose-escalation study designed to determine the safety and dose response of aerosolized C-urea 20 mg and 50 mg in detecting urease-producing bacteria in the lungs of healthy volunteers (those without and those diagnosed with *H. pylori* infection) and in subjects with CF. Subjects will be contacted by telephone the next day and asked a non-leading question about adverse events.

The dose will not be escalated until at least 24 hours after all subjects in the cohort have been tested at the current dose. If a subject has an adverse event or new symptom that remains unresolved at 48 hours, no new subjects will be enrolled until the relationship between the AE and symptom can be evaluated. If any subject experiences an adverse event considered by the data safety monitor to be dose limiting, then three additional subjects will be enrolled at that

current dose. Dose escalation will stop as described in Table 1 if more than one additional subject experiences dose-limiting toxicity (DLT) (Section 3.1.3.1).

After the safety of the maximum dose in the cohort of healthy volunteers without *H. pylori* infection has been reviewed by a data safety monitor, healthy volunteers diagnosed with *H. pylori* infection and subjects with CF will be enrolled. Three subjects diagnosed with *H. pylori* infection will be tested at the maximum dose to assess potential interference of urease producing bacteria in the stomach; subjects infected with *H. pylori* can be enrolled at any time after the safety of the maximum dose in healthy volunteers without *H. pylori* infection has been evaluated, but they will meet the entrance criteria for healthy volunteers without *H pylori* infection. Subjects will be discharged from the study site after 30 minutes or thereafter when oxygen saturation levels and FEV1 values return to baseline and coughing symptoms are resolved. Supportive treatment for symptom resolution, if needed, will be recorded on the case report form (CRF).

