## **Title of Study:**

A Dose-escalation Study to Detect Urease-producing Bacteria in Lungs of Healthy Volunteers and Subjects with Cystic Fibrosis Using Aerosolized C-urea

**Indication:** Use of a C-urea breath test in the qualitative detection of urease-containing bacteria in the respiratory tract and as an aid in the initial and post-treatment detection of respiratory tract infections

**Study Design:** This is a single-center, single-administration, dose-escalation study designed to determine the safety and dose response of aerosolized C-urea 20 mg and 50 mg in detecting urease-producing bacteria in the lungs of healthy volunteers (those without and those diagnosed with *Helicobacter pylori* infection) and in subjects with cystic fibrosis (CF). Subjects will be contacted by telephone the next day and asked a non-leading question about adverse events.

The dose will not be escalated until at least 24 hours after all subjects in the cohort have been tested at the current dose. If a subject has an adverse event or new symptom that remains unresolved at 48 hours, no new subjects will be enrolled until the relationship between the AE and symptom can be evaluated. If any subject experiences an adverse event considered by the data safety monitor to be dose limiting, then three additional subjects will be enrolled at that current dose. Dose escalation will stop if more than one additional subject experiences dose-limiting toxicity.

After the safety of the maximum dose in the cohort of healthy volunteers without *H. pylori* infection has been reviewed by a data safety monitor, healthy volunteers diagnosed with *H. pylori* infection and subjects with CF will be enrolled. Three subjects diagnosed with *H. pylori* infection will be tested at the maximum dose to assess potential interference of urease producing bacteria in the stomach; subjects infected with *H. pylori* can be enrolled at any time after the safety of the maximum dose in healthy volunteers without *H. pylori* infection has been evaluated, but they will meet the entrance criteria for healthy volunteers without *H. pylori* infection.

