**Table 1 Dose Escalation Rules** 

Condition within 24 hours after administration of study drug	Number of DLTs/ Subjects in Cohort	Action
If no subject experiences DLT	0/3	Enroll three subjects at the 50 mg dose level
If one subject experiences DLT	1/3	Enroll three additional subjects at the 20 mg dose
If no additional subject experiences DLT	1/6	Enroll three subjects at the 50 mg dose level
If more than one subject experiences DLT	>1/6	Stop enrollment

Subjects will be receive C-urea 20 mg and 50 mg unless enrollment stops because of DLT. DLT Dose-limiting toxicity.

Sputum will be collected from each subject with CF before administering study drug in order to identify bacterial flora using two standard microbiologic methods. The first is a quantitative method in which colonies are stained and counted, the second is a colorimetric method in which a sample is plated in a medium that changes to a blue color as its pH is increased by the production of ammonia, a by-product of the urease-catalyzed degradation of urea.

The pharmacokinetics of the production of C-carbon dioxide will be characterized by determining the isotopic ratio of C to C in exhaled carbon dioxide of subjects in each part before study drug administration and at 5, 10, and 15 minutes.

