# 3.2.3 Premature Termination of Study

Dose escalation will be stopped if more than one subject experiences DLT at any dose level. The data safety monitor may terminate the study early by stopping enrollment based upon safety concerns

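### The Synopsis and Section 3.1.3 set the DLT stop one event higher than Table 1 and Section 3.2.3, so the rules disagree at two DLTs in six subjects

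*Protocol*

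**What the plan says.** The escalation rule appears in four places in the protocol.

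- **Synopsis, Study Design.** On expansion: "If any subject experiences an adverse event considered by the data safety monitor to be dose limiting, then three additional subjects will be enrolled" at the current dose. On stopping: "Dose escalation will stop if more than one additional subject experiences dose-limiting toxicity". Table 1 is not mentioned.
- **Section 3.1.3.** The same pair of sentences, with a pointer added: "Dose escalation will stop as described in Table 1 if more than one additional subject experiences dose-limiting toxicity (DLT".
- **Table 1.** With 0/3, go to 50 mg. With 1/3, add three subjects at 20 mg. After expansion, "If no additional subject experiences DLT" (1/6), go to 50 mg; "If more than one subject experiences DLT" (>1/6), stop enrolment. There is no row for 2/3 or 3/3.
- **Section 3.2.3.** "Dose escalation will be stopped if more than one subject experiences DLT at any dose level".

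Sections 5.1.6 and 5.1.8 refer dose assignment to Table 1. Section 3.2 describes the DLT stopping rules as mandatory and lists the data safety monitor's discretion separately. Section 8.5 has the monitor decide when the dose may be increased. Section 1.5 carries the design into the cystic fibrosis part: "In part 2, the same dose-escalation study design will assess the safety of inhaled" urea in those subjects.

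**The concern.** In the Synopsis and Section 3.1.3 the stopping sentence follows the one that adds three subjects, so the word *additional* refers to those three. More than one of them means at least two. With the DLT that triggered the expansion, that makes at least three in six. Table 1 and Section 3.2.3 count all DLTs at the dose level and stop at two.

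The threshold is part of a mandatory safety rule, in a study whose primary objective is safety and of which Section 1.5 says "This is the first study in humans of this" breath test. A reader working from the Synopsis, or from the sentence in Section 3.1.3 without turning to the table, would take 2/6 as short of the stop. Because Section 1.5 uses the same design in both parts, the misstatement bears on the step from 20 mg to 50 mg in healthy volunteers and again in subjects with cystic fibrosis.

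A smaller looseness sits beside it. The Synopsis and Section 3.1.3 expand after a dose-limiting event in any subject, and the sample-size text (Synopsis, Sections 3.2.1 and 9.1) expands every dose level with such an event. Read literally, both would also expand at 2/3 or 3/3, where Section 3.2.3 stops and Table 1 is silent.

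**Working it through.** **Enrolment figures.** There are five groups: healthy volunteers at 20 mg and at 50 mg, *H. pylori* volunteers at 50 mg, and cystic fibrosis at 20 mg and at 50 mg. Planned: 5 × 3 = 15. Maximum, with each group expanded once: 5 × 6 = 30. Both agree with Section 9.1, and neither depends on which stopping wording is used.

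**Outcome by outcome, after 1/3 and expansion by three.**

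| DLTs in the added three | Total | Table 1 and Section 3.2.3 | Synopsis and Section 3.1.3 wording |
|---|---|---|---|
| 0 | 1/6 | escalate | stop condition not met |
| 1 | 2/6 | stop | stop condition not met |
| 2 | 3/6 | stop | stop |
| 3 | 4/6 | stop | stop |

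The only disagreement on this path is at 2/6.

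**How often 2/6 would arise.** The protocol states no DLT rate, so p is an assumption, shown over a range. With independent subjects, the chance of exactly one DLT in three is b₁ = 3p(1 − p)². The chance of 1/3 followed by 1/3 at a given 20 mg level is b₁². Once a cohort has been expanded after 1/3, the chance that the added three give exactly one more DLT is b₁.

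| Assumed p | b₁ (given expansion) | b₁² (from the start) |
|---|---|---|
| 0.05 | 3 × 0.05 × 0.95² = 0.135 | 0.018 |
| 0.10 | 3 × 0.10 × 0.90² = 0.243 | 0.059 |
| 0.25 | 3 × 0.25 × 0.75² = 0.422 | 0.178 |
| 0.33 | 3 × 0.33 × 0.67² = 0.444 | 0.198 |
| 0.50 | 3 × 0.50 × 0.50² = 0.375 | 0.141 |

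**Effect if the prose threshold were applied as the only stop.** Let b₀ = (1 − p)³, and treat 2/3 or 3/3 in the first cohort as a stop under both readings.

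- Table 1: P(escalate) = b₀ + b₁b₀.
- Prose threshold: P(escalate) = b₀ + b₁(b₀ + b₁).
- The difference is b₁², the 2/6 path.

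At p = 0.10 the two are 0.906 and 0.965 (difference 0.059). At p = 0.20 they are 0.709 and 0.856 (0.147). At p = 0.50 they are 0.172 and 0.313 (0.141).

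**The case against.** The strongest reply is that nothing in the protocol permits escalation at 2/6. The Synopsis and Section 3.1.3 give a condition under which escalation stops; they do not say it is the only one. Following Table 1 satisfies every statement. Section 3.1.3 names the table in the same sentence, Sections 5.1.6 and 5.1.8 assign doses by it, and Section 3.2.3 repeats its threshold. The data safety monitor sees data daily and decides each increase. A wrong escalation would need both site and monitor to prefer a summary sentence to the named rule.

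This stands as a limit on the consequences: the percentages above are chances of reaching the disputed result, not of escalating wrongly. It does not remove the mismatch. A stopping rule is read as a threshold. The Section 3.1.3 sentence cites a table and then states a threshold the table does not contain, and the Synopsis has no pointer at all.

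A second reply is that high DLT rates are implausible. Section 1.3 reports gram-range inhaled urea without reported adverse effects, Table 2 describes an isotonic solution, asthma is excluded, and Section 3.2 does not expect bronchospasm from isotonic solutions. That is fair, and it makes the low-rate rows the relevant ones. Even so, at p = 0.10 about one expanded cohort in four would land on 2/6.

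On the expansion trigger, the reply largely succeeds. Section 3.2.3 already stops at 2/3 or 3/3, and the maximum of 30 in Sections 3.2.1 and 9.1 is tied to one DLT per dose level, so expansion after a single DLT is evidently meant. This part is only a matter of alignment.

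**Conclusion.** The concern holds and should be fixed. Two statements of a mandatory safety stopping rule set the threshold one DLT higher than Table 1 and Section 3.2.3, and the versions disagree at exactly one result: one DLT in the first three, then one in the added three. That finding rests on the wording alone and needs no assumed rate.

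Its size does depend on the unstated DLT rate: about 2% to 6% per 20 mg level at rates of 5% to 10%, and about 14% to 20% at rates of 25% to 50%, assuming independent subjects with a common rate. The intended rule can be identified and the monitor's role limits the practical risk. The design and the sample size are not in question.

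**What to change.** 1. In the Synopsis (Study Design) and Section 3.1.3, say that three more subjects are enrolled at the dose if exactly one of the first three has a DLT, and that escalation stops if any of the added subjects has a DLT, that is, if there is more than one DLT in total at that dose level. Keep the references to the monitor's judgement, Table 1 and Section 3.1.3.1, and add the pointer to Table 1 in the Synopsis.
2. As a minor alignment, limit the three added subjects in the Synopsis sample-size paragraph and Sections 3.2.1 and 9.1 to dose levels with exactly one DLT in the first three. Add to Table 1 that 2/3 or 3/3 stops enrolment.

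The maximum tolerated dose definition, the dose for *H. pylori* volunteers and the monitor's powers stay as they are. The cost is protocol wording only: one pair of sentences in two places, three sample-size sentences and one table entry. No subjects or procedures are added; planned enrolment stays at 15 and the maximum at 30.

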**Table 1 Dose Escalation Rules** 

Condition within 24 hours after administration of study drug	Number of DLTs/ Subjects in Cohort	Action
If no subject experiences DLT	0/3	Enroll three subjects at the 50 mg dose level
If one subject experiences DLT	1/3	Enroll three additional subjects at the 20 mg dose
If no additional subject experiences DLT	1/6	Enroll three subjects at the 50 mg dose level
If more than one subject experiences DLT	>1/6	Stop enrollment

Subjects will be receive C-urea 20 mg and 50 mg unless enrollment stops because of DLT. DLT Dose-limiting toxicity.

Sputum will be collected from each subject with CF before administering study drug in order to identify bacterial flora using two standard microbiologic methods. The first is a quantitative method in which colonies are stained and counted, the second is a colorimetric method in which a sample is plated in a medium that changes to a blue color as its pH is increased by the production of ammonia, a by-product of the urease-catalyzed degradation of urea.

The pharmacokinetics of the production of C-carbon dioxide will be characterized by determining the isotopic ratio of C to C in exhaled carbon dioxide of subjects in each part before study drug administration and at 5, 10, and 15 minutes.

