# 3.1.3.1 Dose-limiting Toxicity

The following significant respiratory events will be considered DLTs (Rosenfeld et al 2011):

- an absolute decrease from baseline FEV1 of 20% of baseline or greater
- an absolute decrease from baseline oxygen saturation of at least 10%
- an increase from baseline respiratory rate of 10 breaths per minute for more than 2 minutes during quiet breathing
- new wheezes or rales on examination.

In addition to these events that are mandated DLT, the data safety monitor may determine any serious adverse event attributed to study drug to be dose limiting.

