# 6.2 ACTIVE TREATMENT (DAY 1)

- 1. Review inclusion and exclusion criteria.
- 2. Document all medications taken within the last 48 hours.
- 3. Perform a urine pregnancy test on women of child-bearing potential.
- 4. Record 5-minute sitting vital signs measurements (heart rate, systolic and diastolic blood pressure, and body temperature).
- 5. Perform respiratory examination (respiration rate, auscultation [presence of wheezing and crackles], pulse oximetry, and related symptoms, such as cough) (Section 7.2.1).
- 6. Perform spirometry (Section 7.2.1).
- 7. Administer albuterol, only to subjects with CF (Section 5.1.4).
- 8. Perform baseline spirometry  $10 \pm 2$  minutes after administering albuterol to subjects with CF only (Section 7.2.1).
- 9. For subjects with CF only, collect sputum specimen.
- 10. Collect five breath specimens. Record the clock time at which the sample was collected on two self-adhesive stickers. Place one sticker on the collection bag and the other on the CRF (Section 7.1.2.1).
- 11. Administer study drug by inhalation (Section 5.1.3). Record the clock time at the beginning and end of study drug administration.
- 12. Measuring time from the end of the inhalation of study drug, collect breath specimens at  $5 \pm 1$ ,  $10 \pm 2$ ,  $15 \pm 2$  minutes (three specimens at this time point only) after the inhalation of study drug is completed. Record the clock time of each breath collection on two self-adhesive stickers. Place one sticker on the collection bag and the other on the CRF (Section 7.1.2.1).
- 13. Perform spirometry after collecting the breath specimen at 10 and 30 minutes after the end of study drug administration (Section 7.2.1).
- 14. Assess adverse events (Section 8).

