# 6.3 FOLLOW-UP

Twenty-four hours after administration of study drug, subjects will be contacted by telephone and asked a non-leading question to assess adverse events such as "How do you feel after participating in the study?" Additionally, subjects will be asked if they have taken any

medications since receiving study drug. All medications taken from the time of study drug administration until the follow-up assessment will be recorded on the CRF. Subjects who have adverse events at the follow-up visit will be asked to return to the clinic for evaluation.

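### Table 1 counts DLTs over 24 hours, but scheduled objective DLT measurements end at 30 minutes, and two of the four criteria are not fully assessable even then

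*Protocol*

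**What the plan says.** Table 1 applies its rule to a "Condition within 24 hours after administration of study drug". With no DLT among three subjects the action is "Enroll three subjects at the 50 mg dose level". Section 3.1.3 also holds escalation for at least 24 hours after the whole cohort has been tested.

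Section 3.1.3.1 introduces the mandated list with "The following significant respiratory events will be considered DLTs". The list contains:

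- an FEV1 fall "of 20% of baseline or greater"
- "an absolute decrease from baseline oxygen saturation of at least 10" percent
- "an increase from baseline respiratory rate of 10 breaths per minute for more than 2 minutes during quiet breathing"
- new wheezes or rales found on examination.

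The data safety monitor may also rule a serious adverse event attributed to study drug to be dose limiting.

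For measurement, Section 6.2 (step 13) says "Perform spirometry after collecting the breath specimen at 10 and 30 minutes after the end of study drug administration". Section 7.2.2.1 ties respiratory rate and oximetry to those spirometries. At 24 hours, Section 6.3 has subjects telephoned and "asked a non-leading question to assess adverse events". They are also asked about medications taken since dosing. A subject who reports an adverse event is asked to return to the clinic.

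**The concern.** Safety is the primary endpoint, and Section 1.5 describes this as the first human study of the test. Escalation rests on cohorts of three, so one missed event can change the decision. The rule speaks of 24 hours, but the findings it counts cannot be made by telephone. After discharge, a fall in FEV1 or saturation enters the count only if the subject notices something, reports it, returns, and still shows the change or has the event ruled dose limiting. A missed DLT is indistinguishable from no DLT, so the error goes one way, toward escalation. A statement that no DLT occurred within 24 hours would also rest on two unlike kinds of observation.

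**Working it through.** **1. The plan's own numbers.** There are five cohorts: healthy 20 mg, healthy 50 mg, CF 20 mg, CF 50 mg and *H. pylori* 50 mg. 5 × 3 = 15 planned and 5 × 6 = 30 maximum, which agrees with Section 9.1. Section 9.1 says the sample size is not inferential, so there is no power figure to reproduce.

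**2. Each mandated criterion against the schedule** (Table 4; Sections 6.2, 7.2.1.1, 7.2.2.1, 7.2.2.2).

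| Criterion | Scheduled after dosing | Gap |
|---|---|---|
| FEV1 | 10 and 30 min; repeated after albuterol if the last value is reduced | none scheduled from discharge to 24 h |
| Oxygen saturation | with the 10 and 30 min spirometry | same |
| Respiratory rate | with the 10 and 30 min spirometry, by a one-minute count | same; one count cannot show a rise lasting more than 2 minutes |
| New wheezes or rales | only at an assessment where FEV1 has fallen by at least 20% | no routine post-dose examination |

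The last row goes further than a gap in timing. The trigger for listening to the chest is the same 20% fall that is already a DLT under the FEV1 criterion. As scheduled, auscultation therefore cannot add a DLT that FEV1 has not already supplied. Wheezes or rales without that fall can be missed even at 30 minutes.

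**3. After discharge.** The follow-up column of Table 4 holds only concomitant medications and adverse events. The return visit depends on a report by telephone, and neither Section 3.2.2, Section 6.3 nor the Table 4 footnotes say what it measures.

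**4. Direction and possible size.** Let p be the true 24-hour DLT probability and s the share of those DLTs that the schedule detects. The protocol gives neither, so both are assumptions. Under Table 1, escalation follows 0/3, or 1/3 followed by 0/3. With q = p × s:

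P(escalate) = (1 − q)³ + 3q(1 − q)⁵

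For p = 0.20 and s = 1: 0.8³ + 3 × 0.2 × 0.8⁵ = 0.512 + 0.197 = 0.709. For p = 0.20 and s = 0.5, q = 0.10: 0.729 + 0.177 = 0.906.

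| p | s = 1 | s = 0.9 | s = 0.75 | s = 0.5 | s = 0.25 |
|---|---|---|---|---|---|
| 0.20 | 0.709 | 0.752 | 0.814 | 0.906 | 0.973 |
| 0.33 | 0.434 | 0.500 | 0.605 | 0.783 | 0.933 |

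The table shows the direction and how sensitive the rule is. It does not estimate what will happen in this trial.

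**5. What 0/3 can support.** With complete detection the one-sided 95% upper bound on the DLT rate solves (1 − p)³ = 0.05, so p = 1 − 0.05^(1/3) = 0.632. Under the present schedule that bound applies to DLTs measured in clinic or reached through a report, not to all mandated DLTs within 24 hours.

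**The case against.** The follow-up is more than one open question. Every subject is called at 24 hours and asked about medications, so use of albuterol, the named rescue drug, would be picked up. A reported adverse event leads to a clinic return. Escalation waits 24 hours, and enrolment pauses if an event or new symptom is unresolved at 48 hours (Section 3.1.3). The data safety monitor sees data daily (Section 8.5), may treat an adverse event as dose limiting (Section 3.1.3), and may stop escalation at discretion (Section 3.2). Subjects with a reduced FEV1 are measured again and kept until recovery. The protocol expects any bronchospasm to be mild and transient (Section 1.3) and does not expect an isotonic solution to cause it (Section 3.2). Section 9.4 summarises spirometry by time point, so a reader would see when it was measured.

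All of this stands, and it rules out three stronger readings that a reader might infer:

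- **That there is no follow-up to 24 hours.** There is. What is missing is scheduled objective measurement of the mandated criteria.
- **That every delayed reaction is scored as no DLT.** A symptomatic one that is reported can be evaluated and ruled dose limiting. The changes that escape are those not reported, or already resolved and not adjudicated.
- **That almost all the risk goes unobserved, because 0.5/24 = 2.1%.** That is a share of clock time. The documents give no distribution of onset times, so it says nothing about a share of risk.

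The objection does not remove the mismatch. If early onset is the reason for stopping measurement at 30 minutes, the rule and the report should state the period actually measured. The gaps in auscultation and respiratory rate do not depend on late onset at all.

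**Conclusion.** The point holds as an internal mismatch that should be corrected. Table 1 counts DLTs over 24 hours. No mandated criterion has a scheduled objective measurement after 30 minutes, apart from repeat spirometry or delayed discharge in subjects who have not recovered. Two criteria are also not fully assessable within the clinic stay: new wheezes or rales without a 20% FEV1 fall, and a respiratory-rate rise that must last more than 2 minutes.

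The resulting error favours escalation. Its size cannot be calculated from the protocol, and the probabilities shown rest on assumed values of p and s. Nothing in the protocol says that results will be reported as no DLT within 24 hours, so the concern about reporting is a risk that the wording of Table 1 creates, not a stated plan. A reader might also infer that the 24-hour window is itself wrong. The documents do not settle that. They show only that the window and the schedule disagree.

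**What to change.** 1. **Reconcile the passages.** Bring the Table 1 window and the Section 3.1.3.1 criteria into agreement with Table 4 and Sections 6.2, 6.3, 7.2.1.1, 7.2.2.1 and 7.2.2.2, including when auscultation is done and how a rate rise of more than 2 minutes is established. State whether the return evaluation records the DLT criteria. Which window or schedule is right is for the investigator and the data safety monitor to decide.
2. **Report DLTs in two parts.** Give measured criteria up to the last measurement actually taken, and self-reported events up to 24 hours.
3. **Use the planned call.** After the non-leading question, add a short fixed set of respiratory symptom questions. Medication use is already asked.

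The reporting change and the added questions cost some wording and a few minutes on an existing call. Neither alters the 15 to 30 subjects, the doses or the visits. The cost of reconciling the schedule depends on how it is done. The stated follow-up will look less favourable, and prompted questions may raise counts of minor events. Recording prompted events separately from spontaneous ones preserves the non-leading answer.
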